**Table 10.1-1: Part 2 ORR and width of 95% CI [REDACTED]**

ORR (# of Responders)	95% Exact CI
[REDACTED]	[REDACTED]

**Table 10.1-1: Part 2 ORR and width of 95% CI**

95% CI based on Clopper-Pearson method

Combining Part 1 and Part 2 subjects together, about  $250 * 60\% * 1/3 = 50$  participants will be above the cutpoint.

Table 10.1-2 presents the exact 95% CIs for some scenarios of observed ORRs for TMB cutpoint positive (TMB+) subjects for the entire study.

**Table 10.1-2: Part 1 and Part 2 ORR and width of 95% CI**

ORR (# of Responders)	95% Exact CI

## 10.2 Populations for Analyses

For purposes of analysis, the following populations are defined:

Population or analysis data set	Description
All enrolled patients	All subjects who signed an informed consent form and were registered into the IRT system.
All treated patients	All patients who received at least one dose of any study medication.
All treated patients with evaluable baseline tumor biopsy data	All treated patients with evaluable baseline tumor biopsy data will be included in data analyses.

Population or analysis data set	Description
Complete biomarker data set	All treated patients with evaluable mandatory baseline tumor biopsy and at least one post baseline tumor biopsy.
All baseline TMB evaluable patients	All treated patients with evaluable baseline tumor mutational burden.

### 10.3 Statistical and Computational Analyses

The association between ORR and tumor mutational burden will be explored using logistic regression model among treated patients evaluable for tumor mutational burden.

Due to limited participants as compared with the number of biomarkers that will be evaluated for the second co-primary objective, a multiple logistic regression model, or penalized regression methods (Elastic Net, implemented in SAS procedure GLMSELECT) will be used to assess the potential association between candidate biomarkers in peripheral blood and tumor tissue at baseline and on-treatment with clinical efficacy measures. The primary endpoint will be ORR, and other clinical efficacy measures will be analyzed as part of the secondary endpoints.

The analysis of the primary endpoint ORR will take place after the last treated subject is followed for [REDACTED]. Additional survival analysis will be conducted with longer follow up.

The statistical analysis plan will be developed and finalized before database lock and will describe the selection of participants to be included in the analyses, and procedures for accounting for missing, unused, and spurious data. Below is a summary of planned statistical analyses of the primary and secondary endpoints.

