**Rationale:**

Immune checkpoint signaling through the programmed death 1 (PD-1) axis to its ligand (PD-L1) with or without CTLA-4 inhibition significantly dampens anti-tumor immune responses in different tumor types including NSCLC. Unfortunately, not all patients respond to immune checkpoint blockade, therefore there is a compelling need for a better understanding of factors that would predict response and progression.

Emerging science and evidence from multiple studies, including exploratory analyses from the phase 2 study CA209568 (nivolumab + ipilimumab) and phase 3 study CA209026 (nivolumab monotherapy), tumor mutational burden (TMB) was identified as an important potential biomarker (independent of PD-L1) to help identify patients most likely to benefit from immunotherapy.

CA209592 is a two-part, exploratory, phase 2 open-label study aiming to explore potential biomarkers of response, including tumor mutational burden, and their association with clinical benefit when nivolumab + ipilimumab combination is given as primary therapy for advanced or metastatic NSCLC, regardless of PD-L1 expression (Part 1). Part 2 of the study explores the association between TMB (blood and tissue) and clinical efficacy.

In Part 1, changes occurring in candidate biomarkers within the tumor or within the peripheral blood during treatment, or at the time of disease progression, may provide an understanding of the mechanism of action, and the biology of underlying response (efficacy/safety) and/or underlying acquired resistance, which may help inform future combination strategies.

Based on the Part 2 expansion cohort in this study, tumor TMB and blood TMB will be collected at baseline. The association of tissue and blood TMB analyses with clinical outcomes will be assessed independently.

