### **3.2.6      Research Hypothesis**

Immunomodulatory and pharmacodynamic changes in the peripheral blood and tumor tissue are expected in subjects with advanced or metastatic NSCLC receiving nivolumab + ipilimumab. Although no hypotheses will be formally tested, the CA209592 study will characterize the potential association between biomarkers, including tumor mutational burden, in peripheral blood and tumor tissue with clinical efficacy measures, and generate hypotheses for future studies.

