**Table 4-2: Objectives and Endpoints for Part 2.**

Objectives	Endpoints
Primary	

To evaluate the association between baseline tissue TMB/bTMB and clinical efficacy (ORR) for participants in Part 2

	

The clinical efficacy will be measured by the analysis endpoint of objective response rate (ORR). The association of ORR with baseline tissue TMB and bTMB will be assessed

Secondary	

To investigate bacterially generated and human components enteric biomarkers and identify potential associations with clinical outcomes, including safety and efficacy for participants

	

ORR, PFS, OS

Incidence of AES, SAEs, and select AEs

- Objective response rate (ORR):** The proportion of patients with best overall response (BOR) of RECIST 1.1 defined confirmed complete response (CR) or partial response (PR) in a pre-defined study population.
- Disease control rate (DCR):** The proportion of patients with best overall response (BOR) of RECIST 1.1 defined complete response (CR), partial response (PR), or stable disease (SD) in a pre-defined study population
- Duration of response (DOR):** DOR is defined as the time between the date of the first confirmed response (CR/PR) to the date of the first documented tumor progression (per RECIST 1.1) or death due to any cause. Participants who neither progress nor die will be censored on the date of their last evaluable tumor assessment. Participants who started any subsequent anti-cancer therapy without a prior reported progression will be censored at the last evaluable tumor assessment prior to or on the date of initiation of subsequent anti-cancer therapy.

- **Time to response (TTR):** TTR is measured from the time of first dosing date to the time the criteria for CR/PR are first met.
- **Progression free survival (PFS):** PFS is defined as the time from first dosing date to the date of the first documented tumor progression (per RECIST) or death due to any causes. Participants who neither progress nor die will be censored on the date of their last evaluable tumor assessment. Participants who started any subsequent anti-cancer therapy without a prior reported progression will be censored at the last evaluable tumor assessment prior to or on the date of initiation of subsequent anti-cancer therapy.

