#### 2) Type of Participant and Target Disease Characteristics

- a) Subjects with histologically confirmed Stage IV or recurrent NSCLC (per the 7th International Association for the Study of Lung Cancer classification [Goldstraw 2007]), squamous or non-squamous histology, with no prior systemic anticancer therapy (including EGFR and ALK inhibitors) given as primary therapy for advanced or metastatic disease.

Prior adjuvant or neoadjuvant chemotherapy is permitted as long as the last administration of the prior regimen occurred at least 6 months prior to enrollment.

Prior chemoradiation for locally advanced disease is also permitted as long as the last administration of chemotherapy or radiotherapy (which ever was given last) occurred at least 6 months prior to enrollment.

- b) Measurable disease by CT or MRI per RECIST 1.1 criteria. Tumor assessment performed within 28 days of start of study treatment.
- c) All participants must have tissue submitted during screening. This may include either a formalin-fixed paraffin-embedded (FFPE) tissue block or a minimum of 15 unstained tumor tissue slides.

**Part 1:** For cohort assignment purposes (PD-L1 status determination), archival tissue samples  $\leq$  3 months old will be allowed to determine PD-L1 IHC results. Fresh pre-dose biopsy samples (5 cores: 3 in FFPE and 2 in HypoThermosol®) will still need to be submitted.

**Part 2:** a fresh biopsy (preferred) or archival sample ( $\leq$  3 months old) is required for enrollment, but treatment may start before test results are received.

- d) ECOG Performance Status 0 or 1.

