#### **9.6.10    *Tumor Mutational Burden Evaluation in Tissue and Blood Part 2***

Fresh biopsy is preferred or archival sample ( $\leq$  3 months old) are required for enrollment. For archival tissue, FFPE tissue block (preferred) or submission of 15 unstained tumor tissue sections for PDL-1 and TMB testing will be required. If fresh biopsy tissue is obtained, the collection of plasma/serum must be collected within 7 days.

Based on the Part 2 expansion cohort in this study, tumor TMB and blood TMB will be collected at baseline. The association of tissue and blood TMB analyses with clinical outcomes will be assessed independently.

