### 10.3.1 Efficacy Analyses

Endpoint	Analysis Methods
Primary:	
ORR	
In Part 1, logistic regression model and ROC analysis will be used to evaluate tumor mutational burden as a candidate biomarker of ORR of nivolumab and ipilimumab combination therapy.
 
Multiple logistic regression or penalized regression will be used to screen for (baseline and post baseline) biomarkers simultaneously
 
ORR will be calculated for sub-groups identified by logistic or penalized regression methods, and the confidence interval by Clopper-Pearson method will be provided
 
In Part 2, ROC analysis will be used to confirm cutoffs for baseline tissue TMB and blood TMB that identify subjects who will experience therapeutic benefit based on ORR. Logistic regression will be conducted.
 
ORR will be calculated for TMB (tissue and blood) sub-groups and the confidence interval by Clopper-Pearson method will be provided.

Secondary	
DCR, DOR, TTR, PFS, and OS	
The analysis conducted for ORR will be repeated for other efficacy endpoints of interest. For PFS, OS and DOR, for selected patient sub-groups, Kaplan-Meier curves will be provided, and median of time to events and the associated confidence interval will be calculated.
 
Descriptive summary statistics of TTR will be provided for patients with a BOR of CR or PR.

Exploratory	

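### Do the Part 2 TMB analyses need a PD-L1-adjusted estimate to answer the Part 2 objective?

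*Combined protocol and SAP*

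**What the plan says.** Table 4-2 gives the single Part 2 primary objective: "To evaluate the association between baseline tissue TMB/bTMB and clinical efficacy (ORR) for participants in Part 2". Section 3.2.6 sets the inferential frame: "Although no hypotheses will be formally tested".

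The analyses named for TMB are these:

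- Section 10.3, without naming a Part: "The association between ORR and tumor mutational burden will be explored using logistic regression model among treated patients evaluable for tumor mutational burden".
- Section 10.3.1: "In Part 2, ROC analysis will be used to confirm cutoffs for baseline tissue TMB and blood TMB". A one-sentence statement that logistic regression will be done follows, with no covariates listed.
- Section 10.3.1: "ORR will be calculated for TMB (tissue and blood) sub-groups", with Clopper-Pearson intervals.

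The multiple or penalized regression that takes correlated biomarkers together (sections 10.1 and 10.3) is assigned to the second co-primary objective. Only Part 1 has one.

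The Synopsis rationale, drawing on other studies, says "tumor mutational burden (TMB) was identified as an important potential biomarker (independent of PD-L1"). On Part 2 tissue, section 9.6.10 says "submission of 15 unstained tumor tissue sections for PDL-1 and TMB testing will be required".

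**The concern.** The protocol motivates TMB partly as a marker separate from PD-L1, and it reports that response to this combination rises with PD-L1 expression (section 3.1 and Table 3.2.2-3). Part 2 enrols regardless of PD-L1, so each TMB subgroup will mix PD-L1 positive and negative patients. If TMB-high tumors are more often PD-L1 positive, some or all of a TMB odds ratio above 1 could come through PD-L1. None of the three analyses named for Part 2 would show this. A reader could then credit TMB with information that PD-L1 already carries. Since Part 2 tissue appears to be tested for both markers, leaving out an adjusted model looks like an oversight that would cost little to repair.

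**Working it through.** **1. Objective against analysis.**

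| What Part 2 sets out to do | Named analysis | Needs PD-L1? |
|---|---|---|
| Associate tissue and blood TMB with ORR (Table 4-2) | Logistic regression | No |
| Confirm TMB cutoffs (10.1, 10.3.1) | ROC | No |
| Describe ORR above and below the cutoff (10.3.1) | Subgroup ORR, exact intervals | No |
| Show that TMB adds to PD-L1 | None named | Yes, but not a visible Part 2 objective |

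**2. The plan's own figure.** Section 10.1 projects 250 × 60% × 1/3 = 50 TMB-positive participants over both Parts, which reproduces. For Part 2 alone, 150 × 60% = 90 evaluable patients, and 90 × 1/3 = 30 TMB-positive and 60 TMB-negative.

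**3. How far PD-L1 could carry a TMB association.**

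*PD-L1 and ORR.* Rounding back from Tables 3.2.2-2 and 3.2.2-3, cohort Q has about 15/39 responders, of whom about 13/23 were PD-L1 positive. That leaves 2/16 in the rest, and an odds ratio of (13/10)/(2/14) = 9.1. The same steps for cohort P give 12/21 against 6/17, and (12/9)/(6/11) = 2.4. The remainder may include patients with unknown PD-L1.

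*Assumptions not in the documents.* PD-L1 positivity is 50% or 60%. PD-L1 response rates run from 13/23 against 2/16 (the cohort Q derivation) down to 45% against 30%. TMB has no effect within PD-L1 strata. The TMB/PD-L1 odds ratio is 1, 2 or 4.

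*Formula.* With a = 1/3 TMB-positive and b PD-L1 positive, the share q positive for both solves q(1 − a − b + q)/[(a − q)(b − q)] = the assumed TMB/PD-L1 odds ratio. ORR in each TMB group is then the PD-L1-weighted mean.

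*One case in full.* Take b = 0.5, a TMB/PD-L1 odds ratio of 2, and the cohort Q rates. Of the 30 TMB-positive patients, 18.4 are PD-L1 positive and 11.6 negative. Of the 60 TMB-negative, 26.6 and 33.4.

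- ORR, TMB-positive: (18.4 × 0.565 + 11.6 × 0.125)/30 = 39.5%.
- ORR, TMB-negative: (26.6 × 0.565 + 33.4 × 0.125)/60 = 32.0%.
- Unadjusted odds ratio: (0.395/0.605)/(0.320/0.680) = 1.39, a gap of 7.5 points.

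| Assumed TMB/PD-L1 odds ratio | Unadjusted TMB odds ratio over the range of inputs |
|---|---|
| 1 | 1.00 |
| 2 | 1.11 to 1.39 |
| 4 | 1.21 to 1.87 |

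In the worked case 1.39 is not a biased answer to the Part 2 question. Patients above the cutoff really do respond more often there, and that is the association Table 4-2 asks about. It would mislead only if read as the effect of TMB at fixed PD-L1. For scale, the exact 95% interval for 12/30 responders is 23% to 59%.

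**4. What an adjusted estimate would add.** At n = 90 the large-sample standard error of the log odds ratio is 0.45 to 0.47 unadjusted and 0.46 to 0.53 stratified by PD-L1. For 80% power at two-sided 5%, the within-stratum odds ratio would have to be exp(2.80 × 0.46) = 3.6 to exp(2.80 × 0.53) = 4.4. The model can be fitted, but it would seldom settle whether TMB acts apart from PD-L1.

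**5. Where the joint question sits.** Table 4-1 lists tissue TMB, blood TMB and PD-L1 together as Part 1 candidate biomarkers. Section 10.3.1 screens biomarkers simultaneously, and section 10.1 says correlation among them is factored in. Section 5.1 gives Part 1 at least 50 patients in each PD-L1 group. Cutoff confirmation in Part 2 is a coherent division of labour.

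**6. What the text allows one to conclude.** The section 10.3 sentence matches the Amendment 04 entry in the document history (29-Mar-2017), while Part 2 came with Amendment 05 (02-Mar-2018), so it was not written as the Part 2 model. The Part 2 regression sentence lists no covariates, which leaves them open. Section 10.3 describes itself as a summary and defers detail to a SAP. The exploratory rows of Table 4-1 and section 10.3.1, where a supportive TMB and PD-L1 model would naturally sit, are blacked out or not shown.

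**The case for a change.** The strongest reply is that meeting a narrow objective is not enough. The protocol's own case for TMB rests on its separateness from PD-L1, and two extra models would let readers judge it. Naming them before database lock would also stop covariates being picked after the results are seen. The factual core stands: no PD-L1-adjusted Part 2 model is named in the visible text, and the joint screen is not assigned to Part 2. The arithmetic also stands, in that a real TMB/PD-L1 association would raise the unadjusted odds ratio.

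The step from there to a defect does not stand. The independence wording reports other studies' findings and is not an aim of Part 2. The size depends on an association the documents never quantify. Nor is it certain that the data would be complete. In section 9.6.10 the phrase about PD-L1 and TMB testing is attached to archival tissue, whereas fresh biopsy is preferred. The 1% scoring rule in section 9.6 is given under Part 1. Section 6.1 says of the Part 2 sample that it "is required for enrollment, but treatment may start before test results are received", so a PD-L1 result is not a condition of treatment.

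A pooled analysis of both Parts does not change this. Section 10.1 combines them to project 50 TMB-positive participants and to introduce exact ORR intervals for them (Table 10.1-2). Neither use compares TMB groups.

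**Conclusion.** The concern does not hold. Followed as written, the plan gives a sound answer to the Part 2 objective, an overall TMB-ORR association in an exploratory study without formal testing. The unadjusted estimate is the right one for that question. If TMB has no effect within PD-L1 strata, the part carried by PD-L1 runs from nothing (odds ratio 1.00) to 1.87, under assumed TMB/PD-L1 odds ratios of 1 to 4, PD-L1 positivity of 50% to 60%, and PD-L1 response rates partly back-calculated from small cohorts. A supportive model with PD-L1 would be a reasonable option for the SAP, and a later report claiming that TMB acts separately from PD-L1 would need more than the named Part 2 analyses. Neither makes the plan wrong. The judgement rests on the visible text, and nothing here shows that the full plan lacks such a model.

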### 10.3.1 Efficacy Analyses

Endpoint	Analysis Methods
Primary:	
ORR	
In Part 1, logistic regression model and ROC analysis will be used to evaluate tumor mutational burden as a candidate biomarker of ORR of nivolumab and ipilimumab combination therapy.
 
Multiple logistic regression or penalized regression will be used to screen for (baseline and post baseline) biomarkers simultaneously
 
ORR will be calculated for sub-groups identified by logistic or penalized regression methods, and the confidence interval by Clopper-Pearson method will be provided
 
In Part 2, ROC analysis will be used to confirm cutoffs for baseline tissue TMB and blood TMB that identify subjects who will experience therapeutic benefit based on ORR. Logistic regression will be conducted.
 
ORR will be calculated for TMB (tissue and blood) sub-groups and the confidence interval by Clopper-Pearson method will be provided.

Secondary	
DCR, DOR, TTR, PFS, and OS	
The analysis conducted for ORR will be repeated for other efficacy endpoints of interest. For PFS, OS and DOR, for selected patient sub-groups, Kaplan-Meier curves will be provided, and median of time to events and the associated confidence interval will be calculated.
 
Descriptive summary statistics of TTR will be provided for patients with a BOR of CR or PR.

Exploratory	

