- **Overall survival (OS):** OS is defined as the time from first dosing date to the date of death. If a participant didn't die, OS will be censored on the last date the participant was known to be alive.

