### **10.1 Sample Size Determination**

**Part 1:** The planned sample size is approximately 100. Approximately up to 150 participants are expected to be enrolled to achieve 100 treated participants in the trial. For this hypothesis generating study, the sample size is mainly decided by operational feasibility, and sample size calculation is provided to illustrate the design characteristics of the study. Biomarker hypotheses generated from the study will be validated by analyzing data from other ongoing trials or data from future trials.

One of the co-primary objectives is to evaluate tumor mutational burden as a candidate biomarker of clinical efficacy of nivolumab and ipilimumab combination therapy. For this co-primary objective, the primary endpoint that will be used to measure clinical efficacy is objective response rate (ORR). [REDACTED]

One of the co-primary objectives of the study is to investigate the potential association between candidate biomarkers in peripheral blood and tumor tissue at baseline and on-treatment with clinical efficacy measures. For this co-primary objective, the primary endpoint that will be used to measure clinical efficacy is objective response rate (ORR). Patients can be divided into sub-groups by candidate biomarkers. No formal hypothesis testing will be conducted on ORR in overall patient population or in patient sub-groups. However, to evaluate the association between candidate biomarkers with ORR while factoring in the correlation among biomarkers, a multiple logistic regression or a penalized regression method (Elastic Net, implemented in SAS procedure GLMSELECT) may be used to select important biomarkers simultaneously. More specifically,

patient sub-groups can be identified by biomarkers as covariates in the model, and an important sub-group can be chosen based on biomarker effects estimated from the model. For example, the risk of each patient can be calculated based on estimated covariates, and a suitable cutoff point of patient level risk can be used to identify sub-groups of interest. Other methods can be used to define sub-groups. No matter what methods are used, scientific rationales need to be provided to support the patient sub-groups defined. For patient sub-groups identified, ORR and the associated confidence interval will be calculated, and the estimation bias due to selection bias will be adjusted by re-sampling method.

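### The only association model the readable plan offers for PFS and OS is the yes/no one written for ORR; biomarker association with these censored times should use Cox regression

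*Combined protocol and SAP*

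**What the plan says.** Section 10.3.1 gives one analysis rule for the row DCR, DOR, TTR, PFS and OS: "The analysis conducted for ORR will be repeated for other efficacy endpoints of interest". It then adds, for PFS, OS and DOR, that "for selected patient sub-groups, Kaplan-Meier curves will be provided, and median of time to events and the associated confidence interval will be calculated", and promises descriptive statistics for TTR.

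The ORR analysis is set out in the row above: logistic regression and ROC for tumor mutational burden (TMB), Clopper-Pearson intervals for sub-group ORR, and a multi-marker screen: "Multiple logistic regression or penalized regression will be used to screen for (baseline and post baseline) biomarkers simultaneously".

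Section 10.3 gives the same logistic or penalised models for association of candidate biomarkers "at baseline and on-treatment with clinical efficacy measures. The primary endpoint will be ORR, and other clinical efficacy measures will be analyzed" among the secondary endpoints.

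The definitions after Table 4-2 make PFS and OS times from first dose: "PFS is defined as the time from first dosing date to the date of the first documented tumor progression" or death, censored at the last evaluable tumor assessment, while "OS will be censored on the last date the participant was known to be alive". The Part 2 secondary objective is also one of association: to "identify potential associations with clinical outcomes, including safety and efficacy for participants", with PFS and OS among its endpoints.

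**The concern.** Logistic regression and ROC need a yes/no outcome. They cannot be repeated on a censored time until that time has been made binary, and the readable text gives no rule for doing so. The obvious rule, event by data cut-off, ignores when the event happened and how long each patient was followed. Follow-up will be unequal: Section 5.1 sets a minimum of 6 months, and Section 5.3 expects about 48 months from the start of enrollment to the primary analysis. Status at a fixed time, such as 24 weeks, can be observed under that minimum but discards timing and all later events.

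The study exists to find and rank markers. The stake is that real markers for PFS are harder to separate from noise, and that an estimate depends on the date of database lock. There is a further difficulty for on-treatment markers: PFS and OS start at first dose, but the marker is measured only in patients who reach the Week 5 (±1 week) biopsy.

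**Working it through.** **1. The plan's own figure.** Section 10.1 gives 250 × 60% × 1/3 = 50 participants above the TMB cutpoint. It reproduces exactly and implies 250 × 60% = 150 evaluable. The plan uses it for ORR intervals; here it only sets an illustrative size. No event count or power for PFS or OS is readable.

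**2. Inputs.**
- From the documents: median PFS 3.9 and 8.1 months and 1-year OS 69% (Table 3.2.2-2, cohorts Q and P for PFS, Q for OS); minimum follow-up 6 months (Section 5.1); accrual at most 48 − 6 = 42 months (Section 5.3).
- Assumed: exponential times, hazard ratio (HR) 0.6, uniform accrual, two-sided 5% tests. The plan does no formal testing, so power here only measures information.

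**3. Hand check of one extreme.** With hazard λ, minimum follow-up a and accrual A, P(event) = 1 − [exp(−λa) − exp(−λ(a+A))]/(λA). Let 3.9 months be the marker-negative median, a = 6, A = 42.
- Negative: λ = ln2/3.9 = 0.1777, P = 0.954. Positive: λ = 0.6 × 0.1777 = 0.1066, P = 0.884.
- Expected non-events: 4.6 of 100 and 5.8 of 50. About 10 patients carry the whole yes/no comparison.
- Log odds ratio = ln[(0.884/0.116)/(0.954/0.046)] ≈ −1.00; SE = √(1/95.4 + 1/4.6 + 1/44.2 + 1/5.8) ≈ 0.65; z ≈ 1.54; power ≈ Φ(1.54 − 1.96) ≈ 34%. Simulation gives 33%.
- Cox (Schoenfeld), 139.6 events: √(139.6 × 1/3 × 2/3) × |ln 0.6| = 5.57 × 0.511 = 2.85; power ≈ Φ(0.89) ≈ 81%. Simulation gives 79%.

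**4. Simulated power**, with the medians taken as whole-group medians (4000 runs per cell; Wald test for the binary analyses, score test for Cox):

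| Median PFS, method | Accrual 6 mo | 12 mo | 24 mo | 42 mo |
|---|---|---|---|---|
| 3.9, event yes/no | 64% | 58% | 44% | 26% |
| 3.9, 24-week status | 60% | 60% | 58% | 60% |
| 3.9, Cox | 72% | 75% | 78% | 79% |
| 8.1, event yes/no | 51% | 56% | 56% | 48% |
| 8.1, 24-week status | 40% | 40% | 40% | 41% |
| 8.1, Cox | 52% | 60% | 69% | 75% |

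Part of the worst cell belongs to the Wald test: a likelihood-ratio test there gives 33% instead of 26%.

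**5. Longer follow-up.** Section 5.1 announces survival analysis with longer follow-up but gives no length. At an assumed 24-month minimum, yes/no against Cox is about 0% against 82% (median 3.9) and 50% against 81% (median 8.1). At 3.9 months almost every patient has had an event, so the binary outcome no longer discriminates.

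**6. The odds ratio moves with the data cut.** Marker-negative median 8.1 months, HR 0.6, 24-month accrual:
- 6-month minimum: P = 0.746 and 0.578, so OR = (0.578/0.422)/(0.746/0.254) = 0.47.
- 24-month minimum: P = 0.946 and 0.832, so OR = (0.832/0.168)/(0.946/0.054) ≈ 0.28.

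Cox returns 0.60 at both cuts.

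**7. No true effect.** When follow-up is unrelated to the marker, the yes/no Wald test rejects in 2% to 5% of runs and Cox in about 5%. When marker-positive patients are assumed to enter later, yes/no rejects in 14% to 19% and Cox in 5% to 6%. A separate run gave 12% to 18% against 4% to 5%.

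**8. OS.** Over the same accrual range, yes/no gives 25% to 46% and Cox 25% to 52%. With 24 to 36 months' minimum follow-up, 58% to 67% against 58% to 72%.

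**The case against.** The strongest defence is textual. The repeat rule is limited to endpoints of interest, and the next sentences give PFS, OS and DOR Kaplan-Meier methods and TTR summary statistics. DCR is then the only endpoint without its own method, so the rule may be meant for DCR alone. No passage says PFS or OS will be coded yes/no. This reading is available, and a reader who inferred that the plan has chosen logistic regression for PFS, or has no time-to-event analysis at all, would go further than the documents do. But under this reading no model is left for association with PFS or OS, while Section 10.3 extends the association models to the secondary efficacy measures. Kaplan-Meier in sub-groups already selected serves the Part 1 secondary objective; it cannot screen many correlated markers.

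Other points stand in part:
- The association sentence in Section 10.3 is introduced for an ORR-based objective, and the Part 2 secondary objective concerns enteric markers. The link to PFS and OS is short, but it is there.
- Section 10.3 calls this a summary and announces a later SAP, and parts of Section 10 are redacted. Missing detail is therefore weak evidence, and nothing is held against redacted text. The point rests on the stated rule, which an SAP author would inherit.
- The 26% against 79% cell is an extreme corner, not an expected loss. True accrual is unknown.
- A reader might infer that the yes/no analysis produces false positives in general. It does so only if follow-up differs by marker group. The documents do not show that it will, and the size of the drift was assumed.

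**Conclusion.** The point holds in a limited form. Section 10.3.1 is ambiguous, and its literal reading applies a binary analysis to censored times. On either reading, no censoring-aware association model for PFS or OS is readable.

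For PFS the illustrative cost of the literal rule runs from almost nothing (median 8.1 months, 6-month accrual: 51% against 52%) to about 25% against 80% (median 3.9 months, 42-month accrual). It grows further at median 3.9 months with the longer follow-up announced. For OS it is small. These figures rest on exponential times, HR 0.6, a pooled 150 patients with 50 positive, and assumed accrual.

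Severity is modest. PFS and OS are secondary, Section 3.2.6 rules out formal testing, and Section 10.1 says hypotheses will be validated in other trials. It is still worth correcting, because the better method is standard and needs no new data.

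**What to change.** In Section 10.3.1, limit the repeat of the ORR analysis to DCR and add text such as:

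> For PFS and OS, biomarker association will be estimated by Cox regression (penalised Cox for multi-marker screening), with hazard ratios and 95% confidence intervals. Kaplan-Meier curves and medians will be given for selected sub-groups.

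Keep DOR (Kaplan-Meier) and TTR (summary statistics) descriptive, since both exist only in responders. For on-treatment markers, use a landmark after the Week 5 ±1 week biopsy window or a time-dependent covariate. Do not use markers from the progression biopsy as predictors of PFS, because that biopsy follows the event. Carry the same wording into the SAP. Cox is the standard choice here, not the only valid one.

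The cost is wording and slightly more analysis work, with no extra data. A landmark also drops patients whose event comes before it. That share is uncertain, because scheduled scans are every 8 weeks and the Week 5 CT is optional and in Part 1 only.
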